9.4. Laboratory Evaluations

Blood samples for hematology and biochemistry are to be collected at Baseline, Months 1, 3, 6, 9 and 12 and One and Two Weeks Post Last Dose. Urine samples for urinalysis will be collected at Baseline, Months 1, 3, 6, 9 and 12. HbA1c will be measured at Months 1, 3, 6, 9 and 12. All results will be provided using International System of Units (SI).

Descriptive statistics for hematology, biochemistry, urinalysis and HbA1c will be provided for each test parameter and for change from baseline by visit. Shift tables (i.e., low-normal-high at Baseline versus low-normal-high at each post-baseline visit in a 3-by-3 contingency table) will be provided for hematology, biochemistry, urinalysis and HbA1c to assess changes from Baseline in laboratory values by visit. Shift (0.5% change ranging from $<4.0\%$ to $>7.5\%$) from baseline will be summarized for HbA1c by visit. Also shift (<170 , $170-199$, ≥ 200) from baseline for total cholesterol will be summarized by visit.

Separate listings will be provided for all laboratory evaluations (hematology, biochemistry, urinalysis and HbA1c).

This document is confidential.

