13.2. Planned Analyses

13.2.1. Safety Analysis

Adverse Events:

AEs, which include clinical laboratory test variables, will be documented from the time of the first study medication administration from the open label study until the subject's study participation is complete (study discontinuation and up to 30-days follow-up). All AEs that occur after the first study medication application and up to 30 days after the subject's last study medication application will be considered TEAEs.

Each AE will be reported with severity (mild, moderate, severe), seriousness, duration, resolution, action taken, and its relationship with the study medication (related or not related).

Adverse events will be summarized using system organ classification (SOC) defined by Medical Dictionary for Regulatory Activities (MedDRA); the following AEs will be categorized as AESIs in this study (AEs fitting under these categories to be fully described in the SAP):

- Extrapyramidal reactions (i.e. tardive dyskinesia, akathisia)
- Metabolic changes (hyperglycemia/diabetes mellitus, dyslipidemia, weight gain)
- Orthostatic hypotension
- Suicidality
- Leukopenia, neutropenia, agranulocytosis

TEAEs and AESIs will be summarized by severity and by relationship to study medication. Serious TEAEs and TEAEs leading to study termination will be summarized separately.

Other Safety Assessments:

Laboratory values, vital signs, ECG, and physical examination will be summarized descriptively by visit.

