6.1. General Methods

All analyses and outputs will be produced using SAS® version 9.4 or later. Continuous variables will be summarized using the number of observations (n), mean, standard deviation (SD), median, minimum, and maximum. Categorical variables will be summarized using frequency counts (n), and percentages.

All relevant subject data will be included in listings. All subjects entered the database will be included in subject data listings. All by visit summaries will use the nominal visit. Unscheduled visits will not be summarized but will be included in the listings.

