Adverse Events of Special Interest (AESI) for ecopipam include Convulsions, Depression and Suicide/Self Injury, Drug Abuse, Dependence and Withdrawal, Dyslipedaemia, Hepatic Disorders, Hyperglycaemia/New Onset Diabetes Mellitus, NMS, and Psychosis and Psychotic Disorders.

AESI for Parkinsonism include Ataxia, Confusional state, Coordination abnormal, Somnolence, Disturbance in attention, Dyskinesia, Hyperkinesia, Gait disturbance, Memory impairment, Tremor, Vertigo, Agitation, Anxiety, Disturbance in attention, Dystonia, Bradykinesia, Musculoskeletal stiffness, Dysstasia, Gait disturbance, Posture abnormal, Balance disorder, Movement disorder, Movement disorder, Dyskinesia, Muscle rigidity, Coordination abnormal, Muscle contracture, Bradykinesia, Gait disturbance, Terminal insomnia, Nightmare, Poor quality sleep, Sleep disorder, Fatigue, Dizziness, Balance disorder, Restlessness, Amnesia, Confusional state, Dementia, Mental impairment, Speech disorder, Dysphonia, Vocal cord dysfunction, Parosmia, Anosmia, Urinary incontinence, Anxiety, Apathy, Joint stiffness, Reduced facial expression, Confusional state, Flat affect, Constipation, Depression, Dysphagia, Drooling, Fall, Fear of falling, Loss of visual contrast sensitivity, Muscle tightness, Dysgraphia, Dyskinesia, and Weight decreased.

AESI summary tables are listed below:

- AESI for ecopipam overall and by system organ class and preferred term
- AESI for Parkinsonism overall and by system organ class and preferred term.

In this summary, a patient is counted once at the system organ class and once at each preferred term within the system organ class.

- 14) Most common AEs ($\geq 5\%$) first onset experienced during treatment period will be summarized by month and preferred term.
- 15) Most common AEs ($\geq 5\%$) new incidence or ongoing, experienced during treatment period will be summarized by month and preferred term.

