9.6. ECG

The following ECG data will be collected at Baseline, Months 1, 3, 6, 9 and 12:

- PR interval (msec)
- QRS interval (msec)
- QT interval
- QTc interval (msec)
- Overall ECG result (Normal; Abnormal, Not Clinically Significant; Abnormal, Clinically Significant).

An ECG is optional at unscheduled visits, per the investigator's discretion.

The actual ECG results along with change from baseline will be summarized at each visit. Shift (<=450, >450 to <= 480, > 480 to <= 500, >500) from baseline in QTc interval will be summarized by visit. ECG outliers for QTc interval (change from baseline>30 to <=60, >60), PR interval (>25% increase change from baseline,>200, >25% increase change from baseline and PR>200) and QRS interval (>25% increase change from baseline,>200, >25% increase change from baseline and QRS>200) will be summarized by visit and overall. All ECG data will be presented in a listing.

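### Laboratory results are tabulated only visit by visit: no test has a count of children ever abnormal, and neutrophils, liver tests and fasting glucose have no graded classes

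*SAP*

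**What the plan says.** Under SAP 9.4, haematology and chemistry are drawn at Baseline, at five on-treatment visits (Months 1, 3, 6, 9 and 12) and at the two follow-up visits. Four kinds of summary are planned, all by visit:

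- Values and changes: "Descriptive statistics for hematology, biochemistry, urinalysis and HbA1c will be provided for each test parameter and for change from baseline by visit". SAP 6.1 defines the content: "Continuous variables will be summarized using the number of observations (n), mean, standard deviation (SD), median, minimum, and maximum".
- Shifts for haematology, biochemistry, urinalysis and HbA1c: "Shift tables (i.e., low-normal-high at Baseline versus low-normal-high at each post-baseline visit in a 3-by-3 contingency table".
- A second HbA1c shift in 0.5% steps, from below 4.0% to above 7.5%, which "from baseline will be summarized for HbA1c by visit".
- A three-class shift (<170, 170-199, ≥200), which "from baseline for total cholesterol will be summarized by visit".

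All results are also listed. The table index (the 14.3.4.1 series, 14.3.4.8 and 14.3.4.9) holds no other laboratory table.

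Two general rules decide which results reach these tables. SAP 6.1 bases by-visit summaries on the nominal visit and sends unscheduled visits to the listings only. SAP 6.4 keeps one result per window for laboratory data: the one nearest the target day or, in a tie, the high one.

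Heart rate (SAP 9.5) and ECG intervals (SAP 9.6) are handled differently. Values beyond stated thresholds "will be summarized by visit and overall".

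On adverse events of special interest, protocol 13.2.1 names "Leukopenia, neutropenia, agranulocytosis". The SAP 9.3 list omits that group but includes "Hepatic Disorders, Hyperglycaemia/New Onset Diabetes Mellitus, NMS, and Psychosis and Psychotic Disorders".

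**The concern.** The primary objective is long-term safety. The natural question for a laboratory signal is how many children developed it during the year, and how badly. The planned tables answer neither directly for neutrophils, white cells, liver tests or fasting glucose. A transient abnormality that strikes different children at different visits shows as a small percentage each time and is never added up per child. In the shift table, a neutrophil count just under the lower limit shares a cell with a profoundly low one, and a marginally raised ALT shares a cell with a grossly raised one.

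The adverse event tables are not a dependable substitute. Protocol 12.4 lets the investigator decide not to report clinically significant laboratory changes as adverse events, unless they are serious or lead to stopping the drug. Protocol 12.2.1 counts clinical significance, in the investigator's opinion, as grounds for calling an abnormality an adverse event. The two sections pull apart, and both rest on judgement at the site. CTCAE grading in SAP 9.3 applies to adverse events and not to laboratory values. Neutropenia also has no place on the SAP's special-interest list, so beyond the general adverse event tables the laboratory summaries must carry that signal.

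**Working it through.** The plan states no laboratory rate, sample size or incidence on this point, so there is no figure to reproduce. There are two checks.

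**1. What by-visit percentages say about the share ever abnormal.**

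Inputs: k = 5 on-treatment laboratory visits (SAP 9.4), or k = 7 with the two follow-up visits. The per-visit rate p is an assumption, shown over a range because the documents give none. The rate is taken as constant and the data as complete.

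- Same children abnormal at every visit: share ever abnormal = p.
- Different children at every visit: share = k × p.
- Visits independent: share = 1 − (1 − p)^k.

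| k | p (assumed) | Lowest | Independent | Highest |
|---|---|---|---|---|
| 5 | 1% | 1% | 1 − 0.99^5 = 4.9% | 5% |
| 5 | 2% | 2% | 1 − 0.98^5 = 9.6% | 10% |
| 5 | 3% | 3% | 1 − 0.97^5 = 14.1% | 15% |
| 5 | 5% | 5% | 1 − 0.95^5 = 22.6% | 25% |
| 7 | 2% | 2% | 1 − 0.98^7 = 13.2% | 14% |

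In counts, take an illustrative 100 children with 2 abnormal at each of five visits. Identical percentages abnormal at every visit are compatible with 2 children ever affected or with 5 × 2 = 10.

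**2. Whether an extreme value must appear somewhere in the tables.**

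Take the Month 3 window in SAP 6.4: days 71 to 98, target day 85.

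- *Low count at an unscheduled draw on day 90, normal scheduled value on day 85.* SAP 6.1 excludes the unscheduled draw. If SAP 6.4 is read as admitting it, day 85 is 0 days from target and day 90 is 5, so the normal value is kept. The low count is lost either way.
- *Low count at the scheduled visit on day 82, recovered at a retest on day 87.* If retests enter the window, the distances are 3 and 2 days, so the recovered value replaces the low one.
- *Low count on day 82, recovered on day 88.* Both are 3 days from target, so the high value is kept. I read high as the higher result. For neutrophils and white cells that is the less worrying one.

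In each case the low value also drops out of that visit's minimum, because the minimum is taken over the summarized values.

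**The case against.** The strongest reply is that the plan gives more than a bare shift, and much of that stands.

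- A reader might infer that severity is not tabulated at all. The documents do not support this. The minimum and maximum of every test and of its change are given at each visit, so the most extreme summarized ALT or neutrophil count is visible. What is missing is how many children lie in each degree of abnormality. The extreme is also shown only for values that survive the window and unscheduled-visit rules.
- A reader might infer that glycaemia is graded only as low, normal or high. It is not: HbA1c is shifted in 0.5% steps. For hyperglycaemia the gap is the any-time count and the lack of graded fasting glucose. The HbA1c shift has its own limit, since the schedule has no Baseline HbA1c and only in some cases may a parent-study value stand in.
- A reader might infer that the SAP breaks a protocol commitment. Protocol 13.2.1 promises only descriptive summaries of laboratory values by visit, and the SAP delivers those and adds shifts.
- A reader might infer that information is lost. All results are to be listed, unscheduled ones included, so the counts can be derived later.
- Adverse events do catch part of this. Abnormalities that cause symptoms, need intervention or interrupt treatment qualify under protocol 12.2.1, and special-interest events are counted once per patient. What escapes is mainly the asymptomatic value on which nobody acted.
- The special-interest terms come from two lists: neutropenia from the protocol, hepatic disorders from the SAP. That mismatch is a separate matter, and the present point does not depend on it.

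The range from p to 5p is generic to any five-visit table and rests on assumed rates. It shows that the quantity is undetermined, not that many children are affected. None of these replies supplies a count per child.

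**Conclusion.** The point holds as a tabulation gap worth closing. No laboratory test has an any-time or worst-post-baseline count per child. Neutrophils, white cells, ALT, AST, bilirubin and fasting glucose have no graded classes, although the same SAP gives heart-rate and ECG outliers both thresholds and a total across visits. With five on-treatment visits the share ever abnormal can be one to five times the per-visit rate, for example 2% to 10% at an assumed 2%, given a constant rate and complete data. The selection rules can also keep an extreme value, especially a low neutrophil count, out of every laboratory table. The documents do not show that any such signal exists, that data are lost, or that the extent of abnormality is wholly untabulated. Nothing in them explains why these tests were left out when the ECG, heart-rate, HbA1c and cholesterol tables were added after database lock (SAP 10).

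**What to change.** Add one laboratory outlier table to SAP 9.4, laid out like Table 14.3.4.7b with by-visit rows and an overall row, for neutrophils, white cells, ALT, AST, total bilirubin and fasting glucose. Among subjects not already beyond the class at Baseline, give n (%) with any post-baseline value in each class. Fix the classes in writing before the table is run. Possible schemes are CTCAE v4.03 laboratory grades, a version SAP 9.3 already cites for adverse events, or multiples of the upper limit of normal for liver tests. The documents set no cut-offs for these tests, so the sponsor must choose and record them.

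Add a Baseline-versus-worst-post-baseline column to the existing shift tables.

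For the overall row and the worst-value column, state that SAP 6.1 and 6.4 do not restrict the data: every post-baseline result counts, including unscheduled ones and all values within a window. State also that worst means the lowest value for neutrophils and white cells.

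The cost is one table and one set of columns from data already held, labelled post hoc like the other post-lock additions. These are analysis categories only and change no clinical management rule.

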9.5. Vital Signs

Vital sign measurements including sitting systolic blood pressure, sitting diastolic blood pressure, sitting pulse rate, supine orthostatic systolic blood pressure, supine orthostatic diastolic blood pressure, supine pulse rate, standing orthostatic systolic blood pressure, standing orthostatic diastolic blood pressure, and standing pulse rate at each scheduled time and changes from baseline in vital sign measurements will be summarized with descriptive statistics at each scheduled time point.

Body height will be measured at Baseline and will be summarized. Weight will be measured at each schedule visit and, along with changes from baseline, will be summarized with descriptive statistics at each scheduled time point. Weight will be displayed in kilograms; height will be displayed in centimeters.

Body mass index (BMI) will be derived from the weight at each visit and from height (at screening), along with changes from baseline, will be summarized with descriptive statistics at each schedule timepoint.

BMI will be displayed in kilograms per meter squared.

The Centers for Disease Control and Prevention (CDC) growth charts will be used to calculate weight z-score, height z-score and BMI z-scores. Shift (0.5 change ranging from <-3 to >3) from baseline will be summarized for weight z-score, height z-score and bmi-z score by visit. Mean BMI, height and weight z-scores over time will be illustrated in a figure.

Heart rate outliers such as >25% decrease change from baseline, <50, >25% decrease change from baseline and <50 as well as >25% increase change from baseline, >100, >25% increase change from baseline and >100 will be summarized by visit and overall.

All vital signs data will be presented in a listing.

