Children's Depression Rating Scale-Revised (CDRS-R)	X	X	X	X	X	X	X	X	X	X	X	X	X		
Pediatric Anxiety Ratings Scale (PARS)	X	X	X	X	X	X	X	X	X	X	X	X	X		
Adverse Events	X	X	X	X	X	X	X	X	X	X	X	X	X	X	X
Concomitant Medications	X	X	X	X	X	X	X	X	X	X	X	X	X	X	
Dispense Study Drug	X	X	X	X	X	X	X	X	X	X	X	X	X^3		
Collect Unused Study Drug/Assess Drug Compliance		X	X	X	X	X	X	X	X	X	X	X	X	X	

Confidential

Abbreviations: BP = blood pressure, CGI = Clinician Global Impression, CGI-TS-I = CGI Tourette Syndrome of Improvement, CGI-TS-S = CGI Tourette Syndrome of Severity, ECG = electrocardiogram, HbA1c = Hemoglobin A1c

^{*} Baseline is to occur within 30 days of the EBS-101-CL-001 14 Day Follow Up Visit (or longer with the permission of the medical monitor). All Baseline measurements can be taken from the Day 14 Follow Up Visit of the EBS-101-CL-001 study if performed less than 7 days prior to the Baseline visit. In this case, the HbA1c and Urine Drug Screen from the Week 12/Completion Visit of the EBS-101-CL-001 study may be used.

¹ Vital signs will include heart rate, BP, orthostatic BP and heart rate (done supine and then 3 minutes after standing), height and weight.

² Subjects should be in a fasting state (8 hours) for laboratory tests.

³ Study drug dispensation for down titration.

⁴ Assessments for Study Visits may be completed in locations other than study clinic and/or safety and efficacy assessments required at these visits will be made available for remote administration due to restrictions as a consequence of the COVID-19 pandemic or other qualifying event.

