12. ASSESSMENT OF SAFETY

12.1. Safety Parameters

Study Visits may be completed in locations other than clinic and/or via remote administration due to restrictions as a consequence of the COVID-19 pandemic or other qualifying event. Safety will be monitored throughout the study at all visits by repeated adverse event (AE) monitoring, vital signs, the Columbia-Suicide Severity Rating Scale (C-SSRS), the Abnormal Involuntary Movement Scale (AIMS), the Barnes Akathisia Rating Scale (BARS), the Pediatric Anxiety Rating Scale (PARS) and Children's Depression Rating Scale-Revised (CDRS-R). In addition to these assessments, at Baseline, Months 1, 3, 6, 9 and 12 safety will also be monitored by clinical and laboratory evaluations and electrocardiogram (ECG) monitoring. At the Follow Up visit, AE monitoring, the C-SSRS, clinical and laboratory evaluations and vital signs will be assessed. Laboratory evaluations will include hematology, chemistry, urine values and HbA1c. A Follow Up phone call will be conducted 30 days after the last dose of study medication to assess AEs. Additional assessments (all visits except the follow up visit) will include the AIMS, the BARS, the CDRS-R and the PARS. C-SSRS will also be assessed (all visits including the Follow Up visit).

The C-SSRS is a low burden (approximately 5 minutes for completion) instrument to assess both suicidal behavior and ideation. The scale is appropriate for subjects from age 6 through to an elderly population.

The AIMS records the occurrences of tardive dyskinesia (TD) in subjects receiving neuroleptic medications. The test is used to detect TD and to follow the severity over time.

Barnes Akathisia Rating Scale (BARS) scale to assess the severity of drug-induced akathisia. Objective and subjective items in the scale measure the level of subject's restlessness.

Children's Depression Rating Scale-Revised (CDRS-R) is a clinically validated rating scale designed to assess psychiatric signs and symptoms of depressions in children and adolescents.

Pediatric Anxiety Rating Scale (PARS) is a clinician-rated instrument for assessing the severity of anxiety symptoms associated with common anxiety disorders and generalized anxiety in children and adolescents.

Vital Signs:

Vital signs will be collected each clinic visit. They include heart rate, blood pressure, orthostatic blood pressure and heart rate (after being supine for 5 minutes and 3 minutes after standing), height and weight.

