6.2. Key Definitions

Treatment emergent adverse events (TEAEs) are defined as any adverse events that start or increase in intensity on or after the first dose of open-label treatment on Day 1.

Duration of exposure is defined as (Date of Last Dose – Date of First Dose) +1. If date of last dose is unknown, then the date of last clinical visit will be used to impute the date of last dose.

Baseline is defined as the last measurement taken before the first dose of open-label treatment on Day 1.

Change from baseline will be calculated for the post-baseline assessment as post-baseline value – baseline value.

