7.2. Demographic and Other Baseline Characteristics

Demographics and other baseline characteristics will be summarized for the Modified Intent-to-Treat and ITT Set. Summary statistics and by-subject listings will be provided.

Demographics and baseline characteristics will include age, sex, ethnicity, race, weight, height, body mass index (BMI).

Age at Study day 1 = (Study day 1 visit date - date of birth + 1) / 365.25 and truncated to complete years.

Height (in cm) = height (in inches) * 2.54

Weight (in kg) = weight (in lbs) * 0.4536

BMI (kg/m²) = Weight(kg)/[Height(m)²]

Demographics and baseline characteristics will also be summarized by treatment group (ecopipam, placebo and overall) from CL (EBS-101-CL-001) study.

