- Shifts from baseline summaries in BMI z-score, height z-score, and weight z-score will be generated and provided in Table 14.3.4.6a, Table 14.3.4.6b, and Table 14.3.4.6c, respectively. Mean BMI, height, and weight z-scores over time will be illustrated in Figure 14.3.4.6a, Figure 14.3.4.6b, and Figure 14.3.4.6c, respectively.
- A summary of shifts from baseline in 12-lead ECG QTc will be provided in Table 14.3.4.7a. A summary of outliers in 12-lead ECG will be provided in Table 14.3.4.7b.
- A summary of heart rate outliers will be provided in Table 14.3.4.7c.
- Shifts from baseline in HbA1c and total cholesterol will be provided in Table 14.3.4.8 and Table 14.3.4.9, respectively.

This document is confidential.

- Generation of listings for ITT Set: Listing 16.2.4.1b (demographics and baseline characteristics), Listing 16.2.6.1b (YGTSS), Listing 16.2.6.2b (CGI-TS), and Listing 16.2.6.3b (C&A-GTS-QOL).
- Generation of listings for Safety Set: Listing 16.2.9.1 (Height, Weight, and BMI z-scores).
- Generation of figures: mean changes from baseline for C&A-GTS-QOL total score (Figure 14.2.1.4.1a), mean changes from baseline for C&A-GTS-QOL VAS (Figure 14.2.1.4.1b), mean BMI, Height, Weight z-scores over time (Figures 14.3.4.6a, 14.3.4.6b and 14.3.4.6c).

This document is confidential.

11. Reference List

2. [SAS Program \(ages 0 to < 20 years \) | Resources | Growth Chart Training | Nutrition | DNPAO | CDC](#)

This document is confidential.

12. Programming Considerations

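### Raw BMI is computed from one fixed, undefined screening height, so a year of normal growth in children is reported as BMI gain

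*SAP*

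**What the plan says.** SAP 9.5 gives the BMI rule: "Body mass index (BMI) will be derived from the weight at each visit and from height (at screening". BMI and its change from baseline are then summarized at each scheduled time point. The paragraph before it says "Body height will be measured at Baseline and will be summarized", while weight is taken at every scheduled visit. Read together, the two paragraphs let weight vary and hold height fixed.

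The same section plans z-scores from the CDC growth charts, with shifts from baseline by visit, and adds "Mean BMI, height and weight z-scores over time will be illustrated in a figure". SAP Section 10 records these as additions made after database lock: "Shifts from baseline summaries in BMI z-score, height z-score, and weight z-score will be generated". The table index groups the z-score shift tables under a post-hoc label.

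Protocol Table 2, footnote 1, reads "Vital signs will include heart rate, BP, orthostatic BP and heart rate (done supine and then 3 minutes after standing), height and weight", and the vital signs row is marked at every visit from Baseline to Month 12 and at follow-up. Protocol 12.1 agrees: "Vital signs will be collected each clinic visit".

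SAP 6.2 defines Baseline ("Baseline is defined as the last measurement taken before the first dose of open-label treatment on Day 1") but not screening. In the schedule of both documents Visit 1 is Baseline, and there is no screening visit.

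**The concern.** Dividing each visit's weight by one fixed height squared is harmless in adults. In growing children it turns height growth into apparent BMI gain.

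Weight is a live safety question here. Protocol 5.3.1 reports that nearly every child in the earlier pediatric extension put on weight, and Protocol 13.2.1 names weight gain as an event of special interest. The SAP 9.3 list of special-interest events for ecopipam does not include it, so the weight and BMI tables carry more of that question. BMI is the measure that should separate excess gain from growth, and under this rule it cannot. The study has one arm, so no control group cancels the growth term.

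The rule can also hide a fall. The adult obesity studies in Protocol 5.2.2.1 showed dose-dependent weight loss. A child who grows while weight stays flat has a falling BMI, but the table would show no change.

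The wording has two further faults. The fixed height is tied to a visit this study does not have. The statement that height is measured at Baseline conflicts with the protocol and with the SAP's own height z-scores by visit, which need later heights.

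**Working it through.** The plan gives no figure to reproduce. The core of the check is algebra.

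**Formula.** Let W0 and W1 be weight at Baseline and at a visit, H the fixed height, and H1 the true height at the visit.

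- Reported BMI at the visit = W1/H² = true BMI × (H1/H)².
- Relative error in that BMI = (H1/H)² − 1. It is zero if H1 = H and positive if the child has grown.
- (W1/H²)/(W0/H²) = W1/W0, so percent change in BMI equals percent change in weight. This needs no assumption. SAP 6.2 reports change as a difference, so the percentage is not itself an output, but the BMI change then carries no information beyond weight.

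**Inputs.** Age 6 to 18 years (SAP 3.1) and one year of monthly visits (SAP 3.3) come from the documents. Starting heights and growth rates do not; they are assumptions, shown as a range. Growth is taken as steady, month m as m/12 of a year, and the fixed height as the height at open-label Baseline.

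**By visit, from 135 cm**, with ((135 + g·m/12)/135)² − 1:

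| Month | g = 4 cm/year | g = 8 cm/year |
|---|---|---|
| 1 | +0.5% | +1.0% |
| 3 | +1.5% | +3.0% |
| 6 | +3.0% | +6.0% |
| 9 | +4.5% | +9.1% |
| 12 | (139/135)² − 1 = +6.0% | (143/135)² − 1 = +12.2% |

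SAP 6.4 sets the Month 12 target at Day 337, which is 336/365.25 = 0.92 of a year. On that clock the last row becomes +5.5% and +11.2%.

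**Month 12 from other heights:**

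| Starting height | Growth in the year | Error |
|---|---|---|
| 115 cm | 4 to 8 cm | +7.1 to +14.4% |
| 155 cm | 4 to 8 cm | +5.2 to +10.6% |
| 165 cm | 2 cm | +2.4% |
| any | 0 cm | 0 |

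**False gain.** Take a child of 138 cm and 34 kg who grows 6 cm with no true change in BMI.

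- Baseline BMI = 34/1.38² = 17.85.
- The same BMI at 144 cm means a weight of 17.85 × 1.44² = 37.02 kg.
- Reported BMI = 37.02/1.38² = 19.44, a false gain of 1.59 kg/m².

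**Hidden fall.** The same child grows 6 cm and stays at 34 kg.

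- True BMI = 34/1.44² = 16.40, a fall of 1.46 kg/m² or 8.2% of Baseline.
- Reported BMI = 34/1.38² = 17.85, a change of 0.

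**If screening means the parent study's screening.** Assume that visit was 4 to 6 months before open-label Baseline, in a child of 140 cm at Baseline growing 6 cm/year with a constant BMI of 18. Baseline BMI is then overstated by 0.53 to 0.80 kg/m², and the 12-month change by 1.62 to 1.65. If screening means Baseline, the error in the change is 18 × [(146/140)² − 1] = 1.58. The error in the change is about the same under either reading; the parent-study reading spoils Baseline BMI as well.

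**The case against.** The best counter-argument is that raw BMI is a minor output with a safeguard beside it. It is descriptive: no test, threshold or sample size depends on it. It has no table of its own, and its likely home is Table 14.3.4.2.1, the vital signs summary. The SAP also plans weight, height and BMI z-scores against growth charts. Weight and height z-scores do not use the fixed-height BMI, so a reader can compare weight gain with growth. Because height z-scores by visit need repeated heights, the fixed-height sentences may be leftover wording. The size rests wholly on assumed growth, the largest figure pairs the shortest height with the fastest growth, and the age mix is unknown.

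Much of this stands and limits the weight of the point. It does not remove the error. No other sentence overrides the rule for raw BMI, so a programmer who follows the SAP will use a fixed height. The z-score displays are post hoc, and the SAP never says which height enters the BMI z-score; if the BMI of 9.5 is used, it shares the error. That the output is descriptive is a weak defence in a study whose primary objective is safety and whose safety results are all descriptive.

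**Conclusion.** The concern holds. As written, SAP 9.5 overstates BMI for every subject who has grown since the fixed height was taken, and biases the change from baseline upward when growth continues during the study. Direction and mechanism need no assumption. The size does: about 6 to 12% of BMI at Month 12 for 4 to 8 cm of growth from 135 cm, 2.4% for 2 cm from 165 cm, and nothing once growth has stopped. The average effect on the table cannot be stated without the age mix and actual growth.

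The reach is limited to raw BMI and its change, plus the BMI z-score shifts and figure if they take their BMI from the same derivation. Weight, weight change, weight z-score and height z-score are unaffected by the BMI rule. The point should be fixed; it does not threaten the study's other analyses.

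**What to change.** In SAP 9.5:

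- Derive BMI at each visit as weight at that visit divided by the square of height at that visit, both from the same assessment. Baseline BMI uses Baseline height as defined in SAP 6.2. Remove the reference to screening.
- State that height and BMI z-scores use height, weight (for BMI) and age from the same visit.
- Correct the height sentence to say that height is measured at each clinic visit, as in the protocol.
- Where height was not measured, for example at a remote visit, set BMI and BMI z-score to missing for that visit. If another rule is preferred, state it.

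Same-visit height removes the artefact but not the normal change of BMI with age, so the BMI z-score should be read alongside raw BMI.

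The cost is a few wording edits, one derivation, and a rerun of the vital signs summary and any z-score output that used the fixed height. The SAP already lists post-lock changes in Section 10, so this one should be recorded there too. No new data are needed, because the protocol already collects height at each clinic visit.
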